8.3 PATIENT POPULATION FOR ANALYSIS

The population for analysis for the primary, secondary and exploratory endpoints will be the Completer Population which will include all patients who complete all study procedures at Baseline, end of Period 1 and end of Period 2.

The population for safety analysis will be the Safety Population which will include all patients who start study-drug dosing following their baseline visit to the study site. The efficacy analysis will be repeated on the safety population

8.4 ANALYSES

8.4.1 Demographics and Baseline Characteristics

Demographics and baseline characteristics will be presented as data listings and summary statistics.

8.4.2 Safety Analyses

8.4.2.1 Adverse Events

The original terms recorded on the subject's CRF by the Investigator for AEs will be standardized by assigning preferred terms from the Medical Dictionary for Regulatory Activities (MedDRA). The Investigator, however, should ensure that the original terms recorded accurately reflect their intended description. All AEs will be described by individual subject listings and summarized in frequency tables broken down by body system, preferred term and dose group.

8.4.2.2 Vital Signs

Vital signs data will be presented in individual listings. In addition, tabular summaries will be used, as appropriate.

8.4.2.3 Clinical Laboratory Test Results

All clinical laboratory data will be presented as patient listings and summary statistics at each assessment time. Values outside the reference ranges will be flagged. As appropriate, summaries may also include change from Baseline and shift tables.

8.4.2.4 Concomitant Medications

The original terms recorded on the patient's eCRF for concomitant medications will be standardized by using the World Health Organization Drug (WHO Drug) coding dictionary. Concomitant medications will be listed by patient.

8.4.3 Efficacy Analyses

All CPEX tests will be assessed by the centralized CPEX assessor for compliance with prospectively defined CPEX test-protocol criteria.

A two-sided, one-sample t-test is planned for the comparison of VO₂MAX at the end of Period 2 compared to baseline. The secondary and exploratory efficacy endpoints of the study will be examined by appropriate statistical methods as described in the statistical analysis plan.

8.4.4 Pharmacokinetic Analyses

Pharmacokinetic data (PEX, CIS and TRANS) will be listed by patient, and summarized for each sampling timepoint.

8.4.5 Pharmacogenetic Analyses

Pharmacogenetic data (CYP2D6 genotyping at screening) will be listed by patient, and incidences of polymorphisms will be summarized.

8.4.6 Pharmacodynamic Analyses

Hemoglobin A1c data will be presented as patient listings and summary statistics at each assessment time. Values outside the reference ranges will be flagged. As appropriate, summaries may also include change from Baseline and shift tables.

8.4.7 Ongoing Data Review and Analyses

8.4.7.1 Study Monitoring Team

All available data will be presented in listings approximately every 2 months (until the study is completed) following 25% enrollment in the study with an emphasis on observed outcomes related to patient safety and tolerance (*i.e.*, AEs, ADEs, vital signs measurements, ECGs, laboratory assessments, and concomitant medications). These listings will be reviewed by the Study Monitoring Team to determine whether the dosing regimen should be altered during the course of the study or whether any other protocol modifications or actions should be instituted to ensure the safety of the patients.

8.4.7.2 CPEX Analysis Following Completion of Period 1

A snapshot of the database will be taken for the CPEX data (listings and summary statistics) when all patients have completed Week 8. A two-sided, one-sample t-test will be performed for the comparison of VO₂MAX at the end of Period 1 compared to baseline.

8.5 REPLACEMENT POLICY

Patients who withdraw from the study or are discontinued for any reason will not be replaced.

9 ETHICAL AND REGULATORY CONSIDERATIONS

9.1 GOOD CLINICAL PRACTICE

This study will be conducted in accordance with Good Clinical Practice (GCP), as defined by the International Conference on Harmonization (ICH) and in accordance with the ethical

principles underlying European Union Directive 2001/20/EC and the United States Code of Federal Regulations, Title 21, Part 50 (21CFR50).

The study will be conducted in compliance with the protocol. The protocol, any amendments, and the subject informed consent will receive Institutional Review Board/Independent Ethics Committee (IRB/IEC) approval/favorable opinion before initiation of the study. The protocol, amendments, and ICF will also be submitted to regulatory authorities prior to commencing the trial as required.

All potential serious breaches must be reported to the Sponsor immediately. A serious breach is a breach of the conditions and principles of GCP in connection with the study or the protocol, which is likely to affect, to a significant degree, the safety or physical or mental integrity of the subjects of the study or the scientific value of the study.

Study personnel involved in conducting this study will be qualified by education, training, and experience to perform their respective tasks. This study will not use the services of study personnel where sanctions have been invoked or where there has been scientific misconduct or fraud (e.g., loss of medical licensure; debarment). Systems with procedures that ensure the quality of every aspect of the study will be implemented.

9.2 INSTITUTIONAL REVIEW BOARD / INDEPENDENT ETHICS COMMITTEE

Before study initiation, the investigator will have written and dated approval/favorable opinion from the IRB/IEC for the protocol, consent form, subject recruitment materials/process (e.g., advertisements), and any other written information to be provided to subjects. The investigator will also provide the IRB/IEC with a copy of the Investigator Brochure or product labeling, information to be provided to subjects, and any updates. The investigator will provide the IRB/IEC with reports, updates, and other information (e.g., expedited safety reports, amendments, and administrative letters) according to regulatory requirements or institution procedures.

9.3 INFORMED CONSENT

Investigators must ensure that subjects (or, in those situations where consent cannot be given by subjects, the legally acceptable representative) are clearly and fully informed about the purpose, potential risks, and other critical issues regarding clinical studies in which they volunteer to participate. Freely given written informed consent must be obtained from every subject (or, in those situations where consent cannot be given by subjects, the legally acceptable representative) before clinical study participation, including informed consent for any screening procedures conducted to establish subject eligibility for the study.

Subjects unable to give their written consent may be enrolled in the study only with the consent of a legally acceptable representative. The subject must also be informed about the nature of the study to the extent compatible with the subjects' understanding, and should they become capable, they must personally sign and date the consent form as soon as possible. The explicit wish of a subject unable to give his or her written consent, who is capable of forming an opinion and assessing this information to refuse participation in, or to be withdrawn from, the clinical study at any time, should be considered by the investigator.

10 ADMINISTRATIVE CONSIDERATIONS

10.1 COMPLIANCE WITH THE PROTOCOL

The study must be conducted as described in the final IRB/IEC-approved protocol. Documentation of approval, signed by the IRB/IEC chairperson or designee, will be sent to the Sponsor.

10.2 PROTOCOL MODIFICATIONS

Protocol modifications to ongoing studies must be made only after consultation between an appropriate representative of the Sponsor and the coordinating investigator. Protocol modifications must be prepared, reviewed and approved by the Sponsor and by the relevant IRBs/IECs.

All protocol amendments and revisions to the informed consent will be submitted to the Sponsor and to the IRB/IEC. No protocol amendments will be implemented until written approval has been given by the IRB/IEC, except when necessary to eliminate an immediate hazard to study subjects. Administrative letters should also be sent to the Sponsor and IRB/IEC; however, they do not require approval. The protocol, amendments, and ICF will also be submitted to regulatory authorities prior to commencing the trial as required.

If a protocol amendment mandates a revision to the informed consent, the revised consent must be used to obtain consent from subjects currently enrolled in the study if it affects them (e.g., if it contains new information regarding safety), and the revised consent must be used to obtain consent from new subjects before enrollment.

10.3 PROTOCOL TERMINATION

Both the Sponsor and the investigator reserve the right to terminate the study at any time. Should this be necessary, both parties will arrange the procedures on an individual study basis after review and consultation. In terminating the study, the Sponsor and the investigator will assure that adequate consideration is given to the protection of the patient's interests.

10.4 AUDITS, MONITORING AND INSPECTIONS

This study will be monitored by the Sponsor regularly to verify informed consent, source documentation, etc., are collected and stored according to the regulations and the data is entered into the electronic case report forms accurately.

10.5 RECORDS RETENTION AND DATA PROTECTION

The investigator will retain, in a confidential manner, all data pertinent to the study for all treated subjects as well as those entered as control subjects, if applicable. The investigator will retain source documents and accurate case histories that record all observations and other data pertinent to the investigation (e.g., the medical record) for the maximum period required by applicable regulations and guidelines or following institutional procedures. If the investigator withdraws from the study (e.g., relocation or retirement), the records will be transferred to a mutually agreed upon designee, such as another investigator or an IRB. Written documentation of such transfer will be provided to the Sponsor.

The patient's personal data and Investigator's personal data which may be included in the Sponsor database shall be treated in compliance with all applicable laws and regulations.

When archiving or processing personal data pertaining to the Investigator and/or to the patients, the Sponsor shall take all appropriate measures to safeguard and prevent access to this data by any unauthorized third party.

10.6 PUBLICATION OF DATA

The results of this study may be published or presented at scientific meetings. If this is foreseen, the investigator agrees to submit all manuscripts or abstracts to the Sponsor prior to submission. This allows the sponsor to protect proprietary information and to provide comments based on information from other studies that may not yet be available to the investigator.

In accord with standard editorial and ethical practice, the Sponsor will generally support publication of multicenter trials only in their entirety and not as individual center data. In this case, a coordinating investigator will be designated by mutual agreement.

Any formal publication of the study in which input of the Sponsor personnel exceeded that of conventional monitoring will be considered as a joint publication by the investigator and the appropriate Sponsor's personnel. Authorship will be determined by mutual agreement.

12 ABBREVIATIONS

Abbreviation	Definition
6MWT	Six minute walk test
ADE	Adverse device effect
AE	Adverse event
ALP	Alkaline phosphatase
ALT	Alanine aminotransferase
AST	Aspartate aminotransferase
BUN	Blood urea nitrogen
CAD	Coronary Artery Disease
CIS	cis -Hydroxy-Perhexiline
CMR	Cardiovascular Magnetic Resonance
CPEX	Cardiopulmonary Exercise
CPIC	Clinical Pharmacogenetics Implementation Consortium
CPK	Creatine Phosphokinase
CPT	Carnitine palmitoyltransferase
CRO	Contract Research Organization
CYP2D6	Cytochrome P450 2D6
CRF	Case Report Form(s)
ECG	Electrocardiogram or electrocardiographic
EM	Extensive Metabolizer
ESR	Expedited safety report
GCP	Good clinical practice
GLP	Good laboratory practice
HbA1c	Hemoglobin A1c or glycosylated hemoglobin
HCM	Hypertrophic Cardiomyopathy
ICD	Implantable cardiac defibrillator
ICH	International Conference on Harmonisation
IEC	Independent Ethics Committee
IM	Intermediate metabolizer
IND	Investigational New Drug
IRB	Institutional Review Board
LDH	Lactate dehydrogenase
LGE	Late Gadolinium Enhancement
LV	Left ventricular
LVH	Left ventricular hypertrophy
LVOT	Left ventricular outflow tract
MedDRA	Medical Dictionary for Regulatory Activities
MICE	Multiple Ion Channel Effect
MPI	Myocardial Perfusion Imaging
NHLBI	National Heart, Lung, and Blood Institute
NSAE	Non-serious adverse event

Abbreviation	Definition
PET	Positron Emission Tomography
PEX	Perhexiline
PHM	Perhexiline Maleate, when referring to the pharmaceutical formulation
PK	Pharmacokinetic
PM	Poor metabolizer
QTc	Corrected QT interval
QTcF	QT corrected according to Fridericia's formula
SADE	Serious adverse device effect
SAE	Serious adverse event
SCD	Sudden Cardiac Death
SPECT	Single Photon Emission Computed Tomography
SUSAR	Suspected unexpected serious adverse reaction
TdP	Torsade de Pointes
TEE	Trans-Esophageal Echocardiogram
TQT	Thorough QT
TRANS	trans -Hydroxy-Perhexiline
TTE	Trans-Thoracic Echocardiogram
UADE	Unanticipated Adverse Device Effect
ULN	Upper limit of normal
UM	Ultra-rapid metabolizer
VO ₂ MAX	Maximal oxygen consumption
VT	Ventricular Tachycardia

APPENDIX A: CONCOMITANT MEDICATION

The following agents (and drug classes) may have interactions with the effects or metabolism of PEX and should be used with caution:

- Insulin and antidiabetic agents
- Adriamycin
- Anticoagulants, *e.g.* warfarin and phenindione
- Cytochrome P450 2D6 inhibitors or substrates, such as
 - B-Blockers (metoprolol, timolol, alprenolol, carvedilol, bufuralol, nebivolol, propranolol)
 - Selective serotonin (5HT) uptake inhibitors, *e.g.* fluoxetine* and paroxetine*
 - Tricyclic and tetracyclic antidepressants, *e.g.* clomipramine hydrochloride and mirtazapine
 - Antiviral agents, *e.g.* ritonavir* and delavirdine
 - Antimalarials, *e.g.* proguanil and lumefantrine
 - Antinauseants, antiemetics, *e.g.* dolasetron and metoclopramide
 - Narcotic analgesics: *e.g.* codeine, morphine, oxycodone, pethidine and tramadol
 - Neuroleptics: *e.g.* risperidone
 - Cytotoxic drugs: *e.g.* tamoxifen, vinblastine, vincristine, vinorelbine, gefitinib and imatinib
 - Chlorpheniramine, dextromethorphan, ethosuximide, galantamine, tolterodine, celecoxib, cimetidine, terbinafine, bupropion* and moclobemide (RIMA).

* Bupropion, fluoxetine, paroxetine, and ritonavir known to be strong inhibitors of CYP2D6. Any patient who regularly takes one of these medications cannot be enrolled in this study per the protocol-defined inclusion and exclusion criteria. Any subject who is being considered for initiation of therapy with one of these medications during the study should be discussed with the medical monitor prior to initiating the medication.

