2.5 PERHEXILINE THOROUGH QT STUDY

PEX has MICE which might also predict a potential QT prolongation effect. Nevertheless, pro-arrhythmic effects have not been seen to any significant extent in its > 30 year clinical experience. The Australian Therapeutic Goods Administration label notes that the drug may be associated with QT prolongation and has been associated with a single report of TdP.

A thorough QT (TQT) study was done to establish the frequency and degree of PEX effects on the QT/QTcF interval. In that study PEX caused QT prolongation (ΔΔ QTcF of 15.3 and 22.8 msec at mean C_{max} of 278.6 and 677.9 ng/mL, respectively) within the plasma concentration ranges tested in this study. Most of the QTcF prolongation was the result of the ΔΔT_{peak-Tendc} at all timepoints up to and including 8 hours post-dosing. Subsequently the QTcF prolongation was the product of similar, combined effects of the ΔΔT_{peak-Tendc} and ΔΔJ-T_{peakc}. This suggests that PEX has mixed ion channel effects at relevant plasma levels, reducing the effect of hERG inhibition. PEX also had a mild effect on heart rate and AV nodal conduction indicating possible late sodium channel effect. PEX was well tolerated with few AEs and no serious adverse events (SAE); there were no pro-arrhythmic events seen during the study. In view of the QTcF prolongation, enhanced cardiac screening and monitoring for QT prolongation and arrhythmias will be included in this clinical study.

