4.3 EXCLUSION CRITERIA

4.3.1 General Exclusion Criteria:

- a. Pregnant women, women who intend to become pregnant, or woman who are not practicing contraception, either pharmacologically or with a barrier method
- b. Lactating women
- c. CYP2D6 Poor Metabolizer (PM) status, based on genotype known prior to Screening, or as determined by genotype assessed at Screening.
CYP2D6 Poor Metabolizer status will be reported by the central laboratory in the screening report according to CPIC guidelines [Crews *et al.*, 2014].
- d. Any patient who regularly takes a medication known to be a strong inhibitor of CYP2D6 (bupropion, fluoxetine, paroxetine, quinidine, or ritonavir)
- e. Any concomitant disease, condition, or treatment that could interfere with the conduct of the study, or that would, in the opinion of the investigator or sponsor, pose an unacceptable risk to patients and/or interfere with the interpretation of study data.
- f. History of a known toxic or inflammatory peripheral neuropathy, such as mononeuritis multiplex, acute or chronic inflammatory demyelinating polyneuropathy, axonal sensorimotor neuropathies, drug-related neuropathy or neuritis, or diabetic neuropathy (history of a compression neuropathy, such as carpal tunnel syndrome, is acceptable)
- g. Poorly controlled diabetes mellitus (*e.g.*, HbA1c > 9.0%)
- h. Clinically severe chronic obstructive pulmonary disease (*i.e.*, Chronic Obstructive Pulmonary Disease requiring home oxygen or history of intravenous or oral steroid use)
- i. History of a known chronic liver disease including cirrhosis of any cause, or chronic hepatitis B or hepatitis C
- j. History of porphyria
- k. History of recurrent hypoglycemia
- l. Active infection requiring antibiotics
- m. Life expectancy of less than 2 years
- n. Evidence of an active or suspected cancer or systemic treatment within the previous 5 years for a malignancy, except for skin squamous cell or basal cell carcinomas that did not require systemic therapy and are considered to be cured
- o. History of substance abuse, including alcohol or illicit drugs within the past 12 months

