4.3.2 QT Interval-Related Exclusion Criteria

- a. Personal history of congenital long QT syndrome, TdP, or drug-induced long QT
- b. On the basis of the mean of triplicate ECGs at screening or baseline:
 - i. QTcF > 500 msec if QRS ≤ 100 msec
 - ii. JTcF > 410 msec if QRS > 100 msec
- c. Serum potassium < 3.8 mEq/L (may be repeated up to two times during screening after attempts at medical management)
- d. Currently taking a medication with known risk of QT prolongation and TdP as listed in the “Known Risk of TdP” Risk Category on www.crediblemeds.org [Woosley and Romero].
- e. If possessing a pacemaker or Implantable Cardioverter Defibrillator (ICD), ventricular pacing > 10% of the time

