4.7 CONCOMITANT MEDICATION

Some medications or drug classes are known to have potential for adverse interactions with PEX. They may be used in the protocol, but they should be considered with caution. A list of these agents is included in the Appendix A: Concomitant Medication.

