3.4 Baseline Variables

3.4.1 Prior and Concomitant Medication

Prior medications, received up to and including 30 days prior to the start of study medication, and concomitant medications received at any point during the study were to be recorded in the CRF.

Some medications or drug classes are known to have potential for adverse interactions with PEX. Although, their use was permitted in the protocol, they were to be considered with caution. A list of these agents is included in Appendix A of the protocol.

The original terms recorded on the patient's eCRF for concomitant medications will be standardized by assigning preferred terms from the International Non-Proprietary Name drug terms and procedures dictionary for treatments and surgical and medical procedures.

Medication start and stop dates, recorded on the eCRF, will be used to determine programmatically whether the medications were (i) started and stopped prior to the study period or (ii) used during the study period. To implement this, any medication with a reported stop date that is before the first dose of any study medication will be regarded as a (i) Prior medication. Medications that start before the first dose of any study medication and are continued into the study or start on or after the first dose of any study medication or will be regarded as (ii) Concomitant medication.

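### The Appendix A step of consulting the medical monitor before an on-study start leaves out quinidine and Known-Risk-of-TdP drugs, although both bar entry

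*Protocol*

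**What the plan says.** **At entry.** Protocol 4.3.1(d) excludes regular users of strong CYP2D6 inhibitors and names "bupropion, fluoxetine, paroxetine, quinidine, or ritonavir"; the synopsis gives the same five. Protocol 4.3.2(d) excludes a patient "Currently taking a medication with known risk of QT prolongation and TdP as listed in the" Known Risk of TdP category of a public drug list.

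**During the study.** Section 4.7 refers to the agents in Appendix A: "They may be used in the protocol, but they should be considered with caution". Appendix A lists classes to be used with caution, among them "Cytochrome P450 2D6 inhibitors or substrates, such as" a series of named examples. Its footnote goes further for some of them: "Bupropion, fluoxetine, paroxetine, and ritonavir known to be strong inhibitors of CYP2D6", and a patient being considered for one of these "during the study should be discussed with the medical monitor prior to initiating the medication". SAP 3.4.1 restates only the general caution: "Although, their use was permitted in the protocol, they were to be considered with caution".

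**The study drug's own effect.** Section 2.5 gives double-delta "QTcF of 15.3 and 22.8 msec at mean" Cmax of 278.6 and 677.9 ng/mL, and says that cardiac screening and monitoring were strengthened because of it.

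**The concern.** The protocol treats two groups of drugs as unsafe enough to bar entry. Once dosing has begun, it asks for a prior conversation with the medical monitor for only part of the first group and for none of the second. The footnote presents itself as restating the entry criteria, so a site would reasonably take it as the complete list.

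What is at stake is patient safety. A new TdP-risk drug would be added to a study drug that already lengthens QTcF. Quinidine, which 4.3.1(d) itself names as a strong CYP2D6 inhibitor, would be started in patients whose perhexiline clearance depends on that enzyme. In either case no one outside the site need hear of it beforehand.

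**Working it through.** There is no stated figure to reproduce. The check compares lists, searches for any other rule, and then looks at what would catch the problem afterwards.

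**1. Entry list against on-study list**

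| Drug or category | Bars entry | Named in the Appendix A footnote (monitor consulted first) | Other on-study rule |
|---|---|---|---|
| Bupropion | 4.3.1(d) | Yes | General caution |
| Fluoxetine | 4.3.1(d) | Yes | General caution |
| Paroxetine | 4.3.1(d) | Yes | General caution |
| Ritonavir | 4.3.1(d) | Yes | General caution |
| Quinidine | 4.3.1(d) | No | General caution, through the open CYP2D6 class only |
| Known Risk of TdP category | 4.3.2(d) | No | None for the category |

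Footnote coverage of the excluded inhibitors is 5 − 1 = 4. The TdP category has 0 entries in 4.7 and Appendix A.

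**2. Search for a rule elsewhere**

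- 4.2.2(f) holds existing HCM medication at a stable dose. It does not address newly started drugs of these kinds.
- 2.8.3, on mitigating QT prolongation, contains ECG entry limits and dose-adjustment triggers, and nothing on co-medication.
- 4.4.4 (QTcF/JTcF dose rules), 4.6 (withdrawal) and Table 6.2 with its footnotes add no step before a new drug is started.
- SAP 3.4.1 points back to Appendix A.

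**3. What happens after a start**

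After Day 1 and through Day 113, Table 6.2 schedules:

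- medication review at 9 visits: Days 8, 15, 29, 43, 57, 71, 85, 99 and 113;
- ECGs at 8 visits: the same days without Day 8.

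So no ECG is scheduled between Day 1 and the Day 15 visit. After that the nominal spacing is 14 days. With the ±3-day window, two consecutive ECGs can be 46 − 26 = 20 days apart (nominal Days 29 and 43). Perhexiline levels come back 3–5 days after sampling.

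The 4.4.4 triggers leave room above the entry limits:

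- QRS ≤ 100 msec: entry is allowed up to QTcF 500 msec. A hold needs QTcF > 540 msec, or a rise > 75 msec with QTcF > 500 msec. A patient entering at 500 msec can rise by 540 − 500 = 40 msec without a hold.
- QRS > 100 msec: entry is allowed up to JTcF 410 msec. A hold needs JTcF > 450 msec, or a rise > 75 msec with JTcF > 410 msec. The margin for a patient entering at 410 msec is 450 − 410 = 40 msec.

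**4. Exposure relative to the reported QT effect**

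The Period 2 target is 300–500 ng/mL (Table 4.1). Since 278.6 < 300 and 500 < 677.9, it lies between the two mean Cmax values at which 15.3 and 22.8 msec were seen. The comparison is approximate: the target is a level about 12 h after dosing, and the QT study figures are at Cmax.

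**The case against.** The list mismatch is not in dispute. The case for giving it little weight is this.

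- **Quinidine is not without a prior safeguard.** The open CYP2D6 class reaches it, and caution applies before prescribing. The gap is between caution and caution plus a call, and the footnote's own step is advisory. This stands as a description. It does not explain why one of the five inhibitors named together in 4.3.1(d) should be handled more lightly than the other four.
- **The footnote concerns CYP2D6 inhibitors, so TdP drugs were never its subject.** This is fair. For the TdP category the point is a gap in on-study coverage, not an internal contradiction. The gap remains, because no other section fills it.
- **Other safeguards exist.** A CIS:PEX ratio below 0.4 leads to withdrawal at Day 8, and later to evaluation and discussion with the medical monitor. Dosing follows plasma level (Table 4.1), the dose may be lowered at any time, and the overdose sections (4.5, 7.3, 7.10) prompt sites to consider a change in CYP2D6-active medication. All of these act after the new drug has been started. The QT, potassium and ICD criteria lower baseline risk but apply only at entry.
- **The QT figures are for perhexiline alone.** They do not measure the added risk from a second drug. Section 2.5 also reports a single TdP case in the drug's labelling and no pro-arrhythmic events in the thorough QT study. This is right, and it is why no event rate is claimed. The same section still treats the prolongation as reason for stronger precautions.
- **The trial is small and short**, with about 33 patients over 16 weeks of dosing and core-laboratory ECG reading. That limits the expected number of such starts but does not remove the hazard for a patient who has one.

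**Conclusion.** The concern holds. The medical-monitor step covers 4 of the 5 inhibitors that bar entry, and the Known Risk of TdP category has no on-study rule at all. Apart from the general caution on CYP2D6 drugs, every safeguard found acts only once the new drug is on board. The first planned check is the medication review at the next visit, which is Day 8 for a start in the first week.

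This is an omission with a possible safety consequence and should be corrected. It does not touch the endpoint, the power or the analysis. Its frequency cannot be estimated from the documents. Nor can one say how many TdP-risk drugs happen to fall under an Appendix A class, because the external list is not reproduced. The conclusion rests on the protocol and SAP text; the investigator brochure and consent pages were not available and might contain further instructions.

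**What to change.** In section 4.7 and the Appendix A footnote, add two items to the drugs that should be raised with the medical monitor before an on-study start: quinidine, and any drug in the Known Risk of TdP category cited in 4.3.2(d). The wording the footnote already uses for the other four drugs is enough; no new prohibition or procedure is needed.

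The cost is one or two lines of protocol text and occasional calls to the medical monitor.
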